4.1 Dose Limiting Toxicity

DLT evaluable subjects include:

- Part I: All subjects
- Part II: The first three (or six if there is one DLT in the first three) subjects in the following cohorts
 - Q3W cohorts at dose levels that have not previously been tested in Part I
 - Q2W cohorts at each new dose level for the Q2W schema
 - Q1W cohorts at each new dose level for the Q1W schema
- Part III: DLT not applicable

DLT assessment period in Part II is shorter than in Part I, justified by the safety and tolerability data collected during the trial and enabling prompt dose escalation as a part of the 3+3 design of Part II.

- Part I: 63 days (9 weeks) following the first dose of FP-1305
- Part II: 28 days (4 weeks) following the first dose of FP-1305

A DLT is defined as a drug related AE \geq Grade 3 according to NCI-CTCAE version 5.0 occurring during the DLT assessment period and related to FP-1305. The following are exceptions to the rule:

- Grade 3 infusion reactions that resolve within 8 hours from the onset of the reaction are not defined as a DLT
- Grade 3 nausea/vomiting or diarrhea for less than 72 hours with adequate antiemetic and other supportive care are not defined as a DLT
- For thrombocytopenia, haemorrhage is required to qualify grade 3 toxicity as DLT; Grade 4 thrombocytopenia is DLT regardless of haemorrhage
- For neutropenia DLT is as follows,
 - Any neutropenic fever
 - Grade 3 neutropenia persisting $>$ 5 days or Grade 4 neutropenia
- For toxicity judged to be consistent with an acute infusion-related reaction or cytokine release syndrome, DLT will be defined as follows (Sehn 2012):
 - Grade 4 drug-related AE or
 - Grade 3 drug-related AE that cannot be resolved by infusion rate reduction or interruption, or supportive care.
- An AE which, in the opinion of the Investigator, is attributed to a study subject's underlying disease will not be considered a DLT.

In addition, the following are considered DLTs (occurring during the DLT assessment period and related to FP-1305):

- Grade ≥ 2 ALT or AST increase accompanied with bilirubin elevation $>2x$ ULN if baseline value was normal; $>2 \times$ baseline if baseline value was abnormal
- Dose delay of the 2nd cycle due to drug-related toxicity of >14 days

A serious adverse event (SAE) may be considered a DLT according to this section. The severity of the AEs will be codified according to the NCI-CTCAE version 5.0. If the subject has an event that meets the DLT criteria otherwise, but it is not considered to be drug related, then the reason needs to be clearly documented. The sites are requested to report the DLTs via electronic case report form (eCRF) immediately within 24 h an event meets the DLT criteria. In case the eCRF cannot be updated with the DLT (e.g. technical issue), sites are to email to Medical Monitor immediately within 24 h stating a suspected DLT has occurred. The SAE reporting according to [Section 11.4](#) is required in any case to all events that meet the SAE criteria.

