To ensure the safety of the study subjects, the first three subjects at and above the 30 mg/kg dose level will be enrolled stepwise after each has cleared their 28 day DLT observation period. The detailed rules for enrolling the first three subjects on a dose level are described below (4.3.2). If any of the first three subjects dosed at the 30 mg/kg dose level has a DMC verified DLT (see [Section 4.1](#) for DLT definition) within 28 days from the first IMP administration, an additional three subjects will be enrolled on the 30 mg/kg dose level. If a maximum of one of the six subjects experiences a DLT at 30 mg/kg dose level, up to ten subjects will be included in the 30 mg/kg dose level after which the trial can proceed to the next dose level. If at least two of the first three subjects or two of the six subjects experience a DMC verified DLT at the 30 mg/kg dose level, then the MTD has been reached, enrolment to the 30 mg/kg dose level will be placed on hold and dose escalation is terminated. The MTD is defined as the highest dose level, in which the first six subjects were treated with a maximum of one subject experiencing a DLT. Subjects on treatment who have not experienced DLT at that dose level may continue receiving the treatment and the DMC will decide regarding the treatment continuation and possible dose level de-escalation for these particular and DLT experienced subjects. The doses 45 and 100 mg/kg Q3W have the same 3 + 3 dosing rules as described for 30 mg/kg, and if at least two of the first three subjects or two of the six subjects has a DLT, then the MTD has been reached, enrolment to the dose level will be placed on hold, and dose escalation is terminated. If MTD is achieved at the dose level of 30mg/kg Q3W, a reserve de-escalation dose level of 20 mg/kg Q3W may be investigated with the same 3+3 design approach.

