8.9.1 Infusion Reactions

In case of an infusion reaction, the following documentation should be recorded

- 1) Pre-infusion assessment (i.e., the drugs administered, doses, number of previous infusions of the agent, and infusion rates)
- 2) Initial symptoms and course of progression

- 3) Time when the infusion was initiated and time when the infusion reaction began
- 4) Intervention, timing, and subject response
- 5) Time of symptom resolution

Infusion reactions are generally not considered to be DLT, but this judgement should be conducted after each case. Severe (Grade 3 or 4) reactions should be reported within 24 hours to the Sponsor.

Grade 1 infusion reaction (Mild reaction; no infusion interruption or intervention necessary)

Monitor the subject closely or treatment according to the local practise. Consider prophylactic medication (e.g., paracetamol a.k.a. acetaminophen and diphenhydramine) for next administration.

Grade 2 infusion reaction (Moderate reaction leading to infusion interruption but responsive to symptomatic treatment): Interrupt the infusion but maintain vascular access with normal saline. Paracetamol (a.k.a. acetaminophen) and diphenhydramine (or other antihistamine according to local practises) usage is recommended or treatment according to the local practise. However, diphenhydramine (50 mg) and ranitidine (50 mg diluted in 5% dextrose to 20 mL) given together for anaphylaxis are superior to diphenhydramine given alone. Vital sign assessment should be periodically repeated until the subject is stable. Once the symptoms are totally resolved, the infusion may be restarted at maximum 50% of the previous infusion rate. If the symptoms do not recur during 30 minutes of infusion of this slower rate, the infusion rate may be increased to the normal rate. If symptoms recur, the infusion must be stopped, and the amount infused should be reported. Prophylactic medication for the next administration is highly recommended and the infusion rate should be adjusted (see [Section 8.2.1](#) and [Section 8.2.2](#)).

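### Section 4.1 gives two tests for a Grade 3 infusion reaction without saying how they combine, so some reactions can be counted as a DLT or not

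*Protocol*

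**What the plan says.** Protocol Section 4.1 starts from a general rule: "A DLT is defined as a drug related AE" of Grade 3 or higher, within the assessment period and related to FP-1305. A list of exceptions follows. Two of its bullets concern infusion reactions.

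- The first bullet uses time: it takes "Grade 3 infusion reactions that resolve within 8 hours from the onset of the reaction" out of the DLT definition.
- A later bullet uses resolvability. It opens "For toxicity judged to be consistent with an acute infusion-related reaction or cytokine release syndrome, DLT will be defined as follows", then names any related Grade 4 event, or a "Grade 3 drug-related AE that cannot be resolved by infusion rate reduction or interruption, or supportive care". It sets no time limit.

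Section 4.1 does not say which bullet prevails or whether meeting either one is enough.

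Section 8.9.1, on managing infusion reactions, says: "Infusion reactions are generally not considered to be DLT, but this judgement should be conducted after each case". It is not limited by grade and does not refer to 4.1.

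Section 4.3.1 applies the count to the 30 mg/kg level, with the same rules at 45 and 100 mg/kg. "If at least two of the first three subjects or two of the six subjects experience a DMC verified DLT", the MTD has been reached and escalation ends. "If a maximum of one of the six subjects experiences a DLT at 30 mg/kg dose level", the level is filled to ten and the trial may move on. Section 4.3.1 points to Section 4.1 for the DLT definition.

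**The concern.** Occurrence of DLTs in the first 28 days is a primary Part II outcome for new doses (Protocol Section 3.10), and the 3+3 rule works on a margin of one event. Sentinel dosing in Section 4.3.2 depends on the same definition. So does the enrolment halt for delayed toxicities in Section 4.2.5. Sites must report within 24 hours once an event meets the DLT criteria (Section 4.1), so they apply the definition before the DMC sees the case. If one reaction can be classified in two ways, the escalation decision may rest on which bullet was read. If the choice is made after the event, it is made by people who know what it will do to the count.

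The disputed event is not far-fetched. Section 8.9.1 describes Grade 3 and 4 infusion reactions as prolonged and slow to respond to symptomatic treatment. A reaction that lasts beyond 8 hours and then settles with care fits that description.

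**Working it through.** The documents state no operating characteristic for the Part II 3+3 rule, so there is no figure to reproduce. The check has three steps.

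**Step 1: classify a related Grade 3 infusion reaction under each bullet of Section 4.1.**

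| Resolves within 8 h | Resolvable by rate reduction, interruption or supportive care | 8-hour bullet | Resolvability bullet |
|---|---|---|---|
| Yes | Yes | Not a DLT | Not a DLT |
| Yes | No | Not a DLT | DLT |
| No | Yes | Exception not met, so DLT by the general rule | Not a DLT |
| No | No | Exception not met, so DLT by the general rule | DLT |

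The bullets agree in rows 1 and 4 and differ in rows 2 and 3. Row 3 (for example, a reaction that settles at 12 hours with supportive care) is the more plausible of the two. Row 2 is narrow, because the reaction must end within 8 hours without the listed measures having resolved it.

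For Grade 4, Section 4.1 is clear: every related infusion reaction is a DLT. The general remark in 8.9.1 does not carry that over.

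**Step 2: move one event through the rule in Section 4.3.1.**

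- 0/3 to 1/3: from clearing the level to adding three subjects.
- 1/3 to 2/3: from adding three subjects to stopping escalation.
- 1/6 to 2/6: from filling to ten and moving on to stopping escalation.

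**Step 3: illustrate the size.** Let p be the per-subject rate of other DLTs and q the rate of disputed reactions. Both are assumptions. Subjects are treated as independent, the two event types as not occurring in the same subject (so the rate is p + q when disputed events count), and the sentinel gate and replacements are ignored. A level passes on 0/3, or on 1/3 followed by 0/3. With DLT rate r:

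P(pass) = (1 − r)³ + 3r(1 − r)² × (1 − r)³

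Example, p = 5% and q = 2%:

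- r = 0.05: 0.8574 + 0.1354 × 0.8574 = 0.973
- r = 0.07: 0.8044 + 0.1816 × 0.8044 = 0.950

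| Other DLTs, p | Disputed not counted | q = 2% | q = 5% | q = 10% | q = 15% |
|---|---|---|---|---|---|
| 5% | 0.973 | 0.950 | 0.906 | 0.814 | 0.709 |
| 10% | 0.906 | 0.871 | 0.814 | 0.709 | 0.600 |
| 20% | 0.709 | 0.665 | 0.600 | 0.494 | 0.396 |

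The difference between not counting and counting runs from 0.023 (p = 5%, q = 2%) to 0.312 (p = 20%, q = 15%).

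**The case against.** A reader might infer that the two bullets are flatly incompatible and that 8.9.1 sets a third criterion. The documents do not support either reading in full.

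- **Cumulative exceptions.** Both bullets sit in one list of exceptions, and an event that misses one exception can still meet another. On that reading the 12-hour reaction is simply not a DLT. This is a fair reading, so row 3 is ambiguous rather than contradictory. It is not the only reading, because the later bullet is worded as a definition of a DLT and not as an exemption. It also leaves row 2 contradictory.
- **Section 8.9.1.** The sentence is a general remark with no threshold, and it defers to judgement of each case. Grade 1 and 2 reactions fall below the 4.1 threshold anyway, and many Grade 3 reactions are exempted. Section 4.3.1 names 4.1 as the definition for the 3+3 count. So 8.9.1 is not a rival criterion. What stands is that it neither refers to 4.1 nor excludes Grade 4.
- **Safeguards.** The 3+3 count uses DLTs verified by the DMC, the DMC reviews toxicity whenever a DLT is observed (Section 17.2), and Grade 3 or 4 reactions reach the sponsor within 24 hours (Section 8.9.1). These make silent site-by-site counting less likely. They do not tell the DMC which bullet to apply.
- **Experience and scope.** The Part I SAP (Section 12) reports no DLTs in 30 subjects. The Part II SAP (Section 4) says a 30 mg/kg cohort was recruited, and Protocol Section 4.3 makes 45 and 100 mg/kg only possible. The number of affected decisions may be small. However, a count of zero DLTs does not show that no disputed reaction occurred, since such a reaction could have been left uncounted.

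**Conclusion.** The point holds as a gap in a decision rule. Section 4.1 does not determine the DLT status of two of the four kinds of Grade 3 infusion reaction: one is ambiguous, the other contradictory but narrow. DMC verification does not settle the choice.

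Two stronger conclusions should not be drawn. First, a reader might infer that any single reclassified event decides between expansion and stopping. Moving 0/3 to 1/3 only adds three subjects; escalation stops only on a second DLT. Second, a reader might take a true DLT rate of 30% or 40% with half the events disputed, which moves the pass probability from 0.494 to 0.814 or from 0.309 to 0.709. The arithmetic is right, but nothing in the documents supports those rates or that share.

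The shift of about 2 to 31 percentage points is an illustration over assumed rates. If disputed reactions are as rare as 2%, it is only 2 to 4 points.

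**What to change.** Before any further dose-escalation subject is dosed:

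1. Reconcile the two infusion-reaction bullets in Protocol Section 4.1 into one criterion, or state which prevails and whether meeting either is enough. The wording should give a single answer for all four rows of the first table above.
2. Make Section 8.9.1 refer to Section 4.1 for DLT status, so that its remark cannot be read against the Grade 4 rule.
3. Use that one definition for site reporting, the DMC count and the separate DLT table promised in Protocol Section 15.3.4.5. The table list in the Part II SAP (Section 20.1) names no DLT table, so one should be added.

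Which clinical criterion applies is for the sponsor and the DMC to decide. The cost is an amendment to the wording of two sections and one added SAP table. Sample size, visits and the 3+3 thresholds do not change.

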8.3 Treatment Schedule

The treatment period is divided into cycles. Each cycle in Q3W dosing lasts three weeks (21 days). The IMP will be administered on Day 1 of each cycle (Q3W) for up to one year with the possibility to extend the treatment beyond one year according to routine clinical practice (see [Section 8.7.1](#)). If the IMP infusion cannot be administered as scheduled the IMP infusion must be administered as soon as possible. The IMP administration day is counted as Day 1 of the cycle (for delays see [Section 8.7](#)).

Protocol Addendum implements more frequent dosings (Q2W and Q1W). Protocol Addendum requires all relevant national approvals in the countries concerned prior to implementation.

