8.7 Dose Modifications, Infusion Delays, Missed Doses and Special Cases

IMP infusion will be prepared based on the subject's predose weight at each cycle (if not available, the most recent weight should be used). No visit specific dose adjustments are allowed for FP-1305, except for weight change adjustments. However, the maximum amount of FP-1305 in one IMP infusion is 10 g and cannot be exceeded irrespective of the weight-based dose. Guidance will be provided in the Pharmacy Manual to ensure calculated doses do not exceed this limit. If the IMP cannot be administered at the scheduled visit for any reason, the IMP must be administered as soon as possible, below here are instructions for Q3W schema. Instructions for Q2W and Q1W schemas are in Protocol Addendum.

- If the delay is 1 to 7 days, the procedures based on the current visit should be performed, and the subsequent visit will follow 21 days from the date of the infusion that occurred.
- If the delay is more than 7 days, the dose is considered missed, and the next per protocol visit should be brought forward and performed as soon as possible. Note, that the tumour images are still to be taken at every scheduled time point
 - (e.g. if there is an eight day delay for Cycle 4 Day 1, Cycle 4 IMP is considered a missed dose. The infusion given eight days after the original schedule in this case is Cycle 5 IMP dose and the related Cycle 5 procedures should be performed. In addition, tumour imaging of Cycle 4 should be done.) The subsequent visit will follow 21 days from the date of the infusion that just occurred.
 - Cycle 2 is an exception: every effort should be made to ensure that Cycle 2 is not delayed. In unavoidable delay, Cycle 2 IMP administration and the related Cycle 2 procedures should be performed as soon as possible.

Subjects that miss two consecutive scheduled doses (more than 49 days from the previous dose) will discontinue the treatment and enter the follow-up period unless specific consultation and agreement occurs between the investigator, the Medical Monitor and the Sponsor justify continued trial therapy. These decisions must be carefully documented.

Additionally, intra-subject dose change may occur to the recommended Part II/Part III dose after it has been determined. This decision must be carefully documented.

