8.9 Management of Toxicities

All AEs should be graded according to [Section 11.3.1](#) and proper action taken based on the clinical findings and grading.

In the following, when a limit for a laboratory parameter in plasma is indicated and the local practice is to have the test in serum, the equivalent value should be considered, and vice versa.

FP-1305 should be withheld for any of the following adverse event at least possibly related to FP-1305:

- 1) Grade 2 pneumonitis (see [Section 8.9.2.1](#))
- 2) Grade 2 or 3 colitis (see [Section 8.9.2.2](#))
- 3) Grade 2 nephritis (see [Section 8.9.2.3](#))
- 4) Grade 2 liver enzyme elevations (see [Section 8.9.2.4](#))
- 5) Grade 2 or 3 endocrinopathy (see [Section 8.9.2.5](#))
- 6) Grade 2 fibrosis due to liver injury (see [Section 8.9.4](#))
- 7) Any other severe or Grade 3 treatment-related adverse reaction
- 8) Prolonged (> 2 weeks) Grade 2 or intolerable Grade 2 toxicity

FP-1305 must be permanently discontinued for any of the following adverse event at least possibly related to FP-1305:

- 1) Any life-threatening adverse reaction (excluding endocrinopathies controlled with hormone replacement therapy and/or immunosuppressants)
- 2) Grade 3 or 4 infusion reaction (see [Section 8.9.1](#))
- 3) Grade 3 or 4 pneumonitis or Grade 2 recurring pneumonitis (see treatment in [Section 8.9.2.1](#))
- 4) Grade 4 colitis (see [Section 8.9.2.2](#))
- 5) Grade 3 or 4 nephritis (see [Section 8.9.2.3](#))
- 6) Grade 3 or 4 hepatic failure (see [Section 8.9.2.4](#))
- 7) Grade 4 endocrinopathy (see [Section 8.9.2.5](#))
- 8) Grade 3 or 4 fibrosis due to liver injury (see [Section 8.9.4](#))
- 9) Inability to reduce the corticosteroid dose to 10 mg or less of prednisone or equivalent per day within 6 weeks from the initiation of the continuous corticosteroid
- 10) Persistent Grade 2 or 3 adverse reactions (excluding endocrinopathies controlled with hormone replacement therapy and/or immunosuppressants) that do not recover to Grade 0-1 within 6 weeks after the last dosing of FP-1305 and that are considered clinically significant
- 11) Any haematological or non-haematological Grade 3 treatment-related adverse reaction that recurs

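### Part II Q3W escalation: a Cycle 2 delay of more than 14 days cannot be seen within the 28-day DLT window, so this listed DLT criterion never counts or counts too late for the sentinel release

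*Protocol*

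**What the plan says.** Protocol 4.1 adds two items to its Grade 3 rule under the lead-in "the following are considered DLTs (occurring during the DLT assessment period and related to FP-1305". One of them is "Dose delay of the 2nd cycle due to drug-related toxicity of >14 days". The assessment period is given as "Part II: 28 days (4 weeks) following the first dose of FP-1305", against 63 days in Part I.

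Section 8.3 sets the dosing interval: "Each cycle in Q3W dosing lasts three weeks (21 days". Section 8.7 treats other doses that are more than 7 days late as missed, but says "Cycle 2 is an exception: every effort should be made to ensure that Cycle 2 is not delayed". A late Cycle 2 therefore stays Cycle 2, and a long delay to it is a meaningful event.

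The criterion feeds the 3+3 rules for 30, 45 and 100 mg/kg, and for the 20 mg/kg reserve level. Section 4.3.1 counts DMC-verified DLTs within 28 days of the first dose. Section 4.3.2 allows subject 2, then subject 3, then all remaining places to be dosed after successive 28-day periods without a DLT. It treats a subject as evaluable after one dose and 28 days of follow-up, so Cycle 2 need not have been given. DLT occurrence over 28 days is also part of the Part II primary outcome (Protocol 3.10), and SAP Part II section 8 repeats the four-week period.

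**The concern.** A listed DLT criterion should be able to occur, and its status should be known when the decision that depends on it is taken. Here neither is assured. A subject whose Cycle 2 is being withheld for drug-related toxicity on day 28 is, under 4.3.2, evaluable and free of DLT. Nothing in 4.1, 4.3 or the Part II SAP says how a delay still running on that day is handled.

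The toxicity affected is mainly Grade 2. Section 8.9 requires the drug to be withheld for several named Grade 2 events and for "Prolonged (> 2 weeks) Grade 2 or intolerable Grade 2 toxicity". It requires permanent discontinuation, where the reaction is clinically significant and is not a controlled endocrinopathy, for Grade 2 or 3 reactions that "do not recover to Grade 0-1 within 6 weeks after the last dosing of FP-1305". Six weeks is day 42 after a single dose. Grade 2 toxicity could thus end treatment after one infusion while the 3+3 records no DLT. Some Grade 3 events exempted in 4.1 are affected too; for example, "For thrombocytopenia, haemorrhage is required to qualify grade 3 toxicity as DLT". Most other related events of Grade 3 or above still count, as does Grade 2 or higher ALT or AST elevation with raised bilirubin.

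**Working it through.** **Inputs.** Part II window 28 days and Part I window 63 days (4.1); Q3W interval 21 days (8.3); delay threshold more than 14 days (4.1); release after 28 days (4.3.2). The stated periods agree: 4 × 7 = 28, 9 × 7 = 63, 3 × 7 = 21. Day 0 is the first dose.

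**Literal reading.**
- Longest delay visible in the window = window − interval.
- Part II: 28 − 21 = 7 days, half the threshold.
- Part I: 63 − 21 = 42 days, so the criterion can be met.
- The threshold is passed only after day 21 + 14 = 35. The first whole day is 21 + 15 = 36.
- Shortfall in Part II: 35 − 28 = 7 days, or 36 − 28 = 8 in whole days. Moving the day count by one does not close it.

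**Toxicity-onset reading.** With the earliest permitted sentinel dosing on days 0, 28 and 56:

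| Subject | Next release allowed | Delay over 14 days known |
|---|---|---|
| 1 | day 28 | day 36 |
| 2 | day 56 | day 64 |
| 3 | day 84 | day 92 |

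Each release may come 8 days before the information it should depend on. The day-84 release opens up to seven places (10 − 3) without further holds.

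**Which rule catches a delay that is not otherwise a DLT?** Section 4.3.1 stops at two DLTs in the first three or six. Section 4.2.5 halts enrolment at two delayed cases among the first six.

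| In the first six | 4.3.1 if the delay counted | 4.3.1 if it does not | 4.2.5 |
|---|---|---|---|
| One delay, no other DLT | clears (1 of 6) | clears (0) | no halt |
| Two delays, no other DLT | stops | clears (0) | may halt |
| One ordinary DLT, one delay | stops (2 of 6) | clears (1 of 6) | no halt |

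The third row is the gap: no automatic rule responds. In the first row, if the delay is in one of the first three subjects, 4.3.1 would have required three more before expansion. As written, the remaining places open at once. In the second row, 4.2.5 says may halt because it speaks of events after the window, and toxicity that began inside it may not qualify.

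**The case against.** The strongest reply is that the consequence is contained:

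- **Escalation gate.** Section 4.3 requires all ten subjects at 30 mg/kg to be enrolled before 45 mg/kg opens, and likewise before 100 mg/kg. The last sentinel's delay is known by day 92 on the earliest schedule, so the DMC would normally know of it before escalating.
- **DMC.** Under 17.2 the DMC reviews toxicity in Part II. It can stop escalation, add an intermediate level or discontinue a cohort. The releases in 4.3.2 are permissions, not obligations.
- **Deliberate window.** Section 4.1 justifies the shorter period by accumulated tolerability data, and 4.2.5 was written for late events.
- **Limited remaining use.** SAP Part II section 4 says a 30 mg/kg cohort was recruited, and 45 and 100 mg/kg are only possible levels.

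All of this stands as a limit on consequence. None of it makes the criterion work. The gate and the DMC give time and discretion but do not put a delay into the 3+3 count. The reason for 28 days does not address a criterion that needs more than 35.

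A reader might infer that a dose with prolonged Grade 2 toxicity would pass straight to the next level. The gate and DMC review do not support that. A reader might also want a probability of wrongly clearing a dose. The documents give no Part II rate for DLTs or delays, and any such figure would apply only if delays never count. The Part I SAP reports no DLT in 30 subjects, but at 10 mg/kg or less, so that does not bound the rate at 30 to 100 mg/kg.

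**Conclusion.** The point holds for the Part II Q3W levels in 4.3. At most 7 days of delay can be seen in a window where more than 14 are required. On the onset reading, the answer comes about 8 days after the release that should depend on it. This rests only on the 21-day interval and the 28-day window; no event rate is assumed. The practical effect is modest. It concerns mainly Grade 2 toxicity withholding Cycle 2, plus some exempted Grade 3 events. The clearest failure is one ordinary DLT plus one Cycle 2 delay, which no rule catches.

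Two extensions should not be drawn:

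- The same arithmetic touches Q2W (14 + 14 = 28, not more than 28 − 14), but the dosing rules for that schedule are in an Addendum not available here, so the point is confined to Q3W.
- Section 4.3.2 bars dosing of subject 2 or 3 after an earlier DLT, which might be read as leaving no route forward. Section 4.3.1 does give one (three more subjects) and 17.2 provides DMC review. That is a wording conflict that defaults to a pause and loses no DLT.

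**What to change.** **Section 4.1, Part II Q3W.** Count as a DLT any drug-related toxicity that starts within 28 days of the first dose and delays Cycle 2 by more than 14 days, or means Cycle 2 is never given because of that toxicity. Date it by toxicity onset, so the 28-day primary outcome wording can stay. State whether infusion reactions exempted in 4.1 remain exempt, because 8.9 stops the drug permanently after any Grade 3 reaction and the never-given clause would otherwise capture them.

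**Section 4.3.2.** If Cycle 2 is being withheld for drug-related toxicity on day 28, hold the next release (subject 2, subject 3 or the remaining places) until Cycle 2 is given or the delay exceeds 14 days.

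**Clarification only.** State in 4.3.2 how dosing resumes under 4.3.1 after a DMC-verified DLT in subject 1 or 2.

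**Cost.** No extra patients. The hold adds at most about 8 days (36 − 28) per affected subject, or 7 (35 − 28) if Cycle 2 is given in time. Full holds cannot accumulate across all three sentinels: each one that runs its course is itself a DLT, and a second stops the level. Prolonged Grade 2 toxicity could then stop a dose, which is what the listed criterion is for.
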